9.6.3 Data collected

9.6.3.1 HCP questionnaire

HCPs practice information:

- Duration of practice (years working with diabetic patients)
- Specialty (GP, endocrinologist/diabetologist, pharmacist, internist, gastroenterologist, nurse, geriatrist)
- Type of setting (office based, hospital based, both, outpatient pharmacy, hospital pharmacy, diabetes care clinic)
- Past experience with SULIQUA (number of patients treated with SULIQUA pre-filled pen)

Information related to the HCP knowledge about the prescribing conditions and safety information/warnings of SULIQUA data include:

- HCP knowledge about SULIQUA pre-filled pen guide for HCPs
- Awareness of the responsibility to provide each patient with the guide for patient treated with SULIQUA
- Knowledge of the instructions for appropriate utilization of SULIQUA pre-filled pen (dose titration, pen choice, storage, adverse reactions)
- Appropriate labelling of dose range and strength of SULIQUA pre-filled pen and dose steps to be administered in prescription (yes/no)
- Education of the patient with regard to dose steps required, design, features and appropriate utilization of SULIQUA pre-filled pen, close blood sugar levels monitoring after initiation, safety information
- Number of recorded medication errors since EM distribution

9.6.3.2 Patient questionnaire

- Patients characteristics (age, gender, length of SULIQUA treatment)
- Treating physician (GP, endocrinologist/diabetologist, internist, gastroenterologist, geriatrist)
- Patient knowledge about SULIQUA pre-filled pen guide for patient (yes/no)

- Patient knowledge about SULIQUA pre-filled pen conditions of use (features and appropriate utilisation of SULIQUA pre-filled pen, close blood sugar levels monitoring after initiation, safety information)

9.6.4 Site/Investigators questionnaire

Not applicable

9.6.5 Patient data

Not applicable

9.6.6 Logistic aspects

For patient questionnaires, each recruiting HCP will hand over a patient kit. Refill of patient kits will be done at HCP's request. In the kit, the patient will find the survey questionnaire with a prepaid envelope for sending the survey back to IQVIA. It will also include a simplified guide for taking the survey online according to the patient's personal choice.

The patient questionnaire completion is estimated to take 15-20 minutes.

9.7 DATA ANALYSIS

The statistical analyses will be described and further detailed into a Statistical Analysis Plan (SAP). The described analysis below might be revised, and adjustments might occur. The final SAP version will include (empty) table shells to be populated for the clinical study report (CSR).

General considerations:

The statistical analysis will be conducted using the SAS[®] software V9.4 on Windows[™] (SAS Institute, North Carolina, US).

Continuous variables will be described by their number (of valid cases, of missing values), mean, standard deviation, median, Q1, Q3, minimum and maximum. Categorical variables will be described as the total number and relative percentage per category. Confidence intervals of 95% will be evaluated, when relevant. The number of missing data will be indicated. Since, missing values are expected to be few and distributed at random, no replacement or imputation will be performed. Missing values will not be considered in the denominators for proportions.

For HCP questionnaire measures, results will be stratified by country and physician's specialty. For patient questionnaire measures, results will be stratified by country and treating physician's specialty. In tables "Overall - unweighted" columns and lines will show the results observed on the sample while "Overall weighted" columns and rows will show the results weighted according to the distribution of HCPs in the general population by country and specialty, respectively.

Two interim and 1 final analysis corresponding to 3 waves of survey will be performed according to timelines (Section 6) in selected European countries.

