8 RESEARCH QUESTION AND OBJECTIVES

The research questions for this study is: Were the key safety messages in the healthcare professional guide and the patient guide, implemented as risk minimisation measures (RMM) beyond routine, effective in:

- Providing a good knowledge and understanding to health care professionals (HCPs) who prescribed or dispensed SULIQUA and to patients treated with SULIQUA
- Reducing the risk of medication errors when prescribing/delivering or using SULIQUA

The main objective of this study is to assess the knowledge and understanding of the key safety messages in the healthcare professional guide and patient guide among HCPs who prescribed or dispensed SULIQUA and patients treated with SULIQUA, respectively.

Specific objectives are to assess the proportion of:

- HCPs:
 - Who receive, understand and implement the safety messages conveyed by EM for SULIQUA
 - Who are aware that prescriptions for SULIQUA should state clearly the dose range and strength of SULIQUA in a pre-filled pen and the number of dose steps to be administered by the patient
 - Who advise patients with regard to dose steps required, design, features and appropriate utilization of SULIQUA pre-filled pen, close monitoring of blood sugar levels after initiation, and anticipated adverse reactions
 - Who noted medication errors in treated patients
- Patients/caregivers
 - Who acknowledge receiving SULIQUA pre-filled pen guide for patients and caregivers
 - Who read the patient guide before using SULIQUA pre-filled pen
 - Who implemented the safe utilisation of SULIQUA according to safety information for the SULIQUA pre-filled pen
 - Who were trained/advised by their HCP (physician or pharmacist) on how to use SULIQUA pre-filled pen

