9.3.1 Collected/estimated through the HCP questionnaire

- Information related to HCPs/patients participation: contact rate, response rate, cooperation rate, and refusal rate (section 9.7)
- Variables related to HCPs practice information:
 - Duration of practice (year working with diabetic patients)
 - Specialty (GP, endocrinologist/diabetologist, pharmacist, internist, gastroenterologist, nurse, geriatrist)
 - Type of setting (office based, hospital based, both, outpatient pharmacy, hospital pharmacy, diabetes care clinic)

- Past experience with SULIQUA (number of patients treated with SULIQUA pre-filled pen)
- Variables related to the HCPs knowledge about the prescribing conditions and safety information/warnings of SULIQUA data include:
 - HCP knowledge about SULIQUA pre-filled pen guide for HCPs
 - Awareness of the responsibility to provide each patient with the guide for patient treated with SULIQUA
 - Knowledge of the instructions for appropriate utilization of SULIQUA pre-filled pen (dose titration, pen choice, storage, adverse reactions e)
 - Appropriate labelling of dose range and strength of SULIQUA pre-filled pen and dose steps to be administered in prescription (yes/no)
 - Education/Advice of the patient with regard to dose steps required, design features and appropriate utilization of SULIQUA pre-filled pen, close blood sugar levels monitoring after initiation, safety information
 - Number of recorded medication errors since EM distribution
- Receipt of SULIQUA pre-filled pen guide for HCPs (yes/no)
- Distribution to patients/caregivers of the guide for patient treated with SULIQUA (yes/no)

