9.7.1 Primary analysis

Distribution of all possible answers

As some questions may have multiple choices or be opened fields, the proportion of HCPs/patients having provided each possible answer will be described (Table 4).

Table 4: Mock table: Distribution of HCPs/patients answers to Question XX by country and physician specialty

Specialty	Answer	Country			Overall unweighted n(%)	Overall weighted * %
		Country 1 (N=XX)	Country 2 (N=XX)	...		
GP (N=XX)	Answer 1	xx (xx.xx)	xx (xx xx)	xx (xx xx)	xx (xx xx)	xx xx
	Answer 2	xx (xx.xx)	xx (xx xx)	xx (xx xx)	xx (xx xx)	xx xx
	...	xx (xx.xx)	xx (xx xx)	xx (xx xx)	xx (xx xx)	xx xx
	Missing	xx	xx	xx	xx	-
Endocrinologist (N=XX)	...	xx (xx.xx)	xx (xx xx)	xx (xx xx)	xx (xx xx)	xx xx
Internist (N=XX)	...	xx (xx.xx)	xx (xx xx)	xx (xx xx)	xx (xx xx)	xx xx
Gastroenterologist (N=XX)	...	xx (xx.xx)	xx (xx xx)	xx (xx xx)	xx (xx xx)	xx xx
Other (N=XX)	...	xx (xx.xx)	xx (xx xx)	xx (xx xx)	xx (xx xx)	xx xx
Overall unweighted (N=XX)	Answer 1	xx (xx.xx)	xx (xx xx)	xx (xx xx)	xx (xx xx)	xx xx
	Answer 2	xx (xx.xx)	xx (xx xx)	xx (xx xx)	xx (xx xx)	xx xx
	...	xx (xx.xx)	xx (xx xx)	xx (xx xx)	xx (xx xx)	xx xx
	Missing	xx	xx	xx	xx	-
Overall weighted	Answer 1	xx xx	xx xx	xx xx	xx xx	xx xx
	Answer 2	xx xx	xx xx	xx xx	xx xx	xx xx
	...	xx xx	xx xx	xx xx	xx xx	xx xx

* According to the distribution of HCPs in the general population by country and specialty, respectively.

Note: This template might be modified, final table shells will be presented in the statistical analysis plan (SAP).

Definition of success

Three success factors for professionals treating patients with SULIQUA will be defined:

1. Proportion of HCPs receiving the EMs (Question Q1 of HCP questionnaire).
2. Proportion of HCPs sufficiently understanding the key messages, i.e. providing at least 75% of correct answers (Questions Q3-Q4, Q7 of HCP questionnaire; at least 11 correct or consistent answers out of 14 sub-questions).
3. Proportion of HCPs adequately implementing the EMs, i.e. providing at least 75% of answers that are correct or consistent with appropriate use of the EMs (Questions Q2a-b, Q5-Q6 of HCP questionnaire; at least 12 correct or consistent answers out of 15 sub-questions).

Three success factors for patients/caregivers will be as follows:

1. Proportion of patients/caregivers receiving the EM (Question Q5 of Patient/Caregiver questionnaire).

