2	Guide for patients and/or caregivers	 Yes  No  I do not remember
3	Letter - Important prescribing information	 Yes  No  I do not remember

Data: single punch per row

Ask Q2a only if response to 1 is yes

Ask Q2b only if response to 2 is yes

Key message:

Sanofi should deliver educational material to Healthcare professionals according to the additional risk minimization measures described in the Suliqua Risk Management Plan.

Q2a. Please answer to the following questions related to the use of the Guide for Healthcare Professionals:

	Use of educational materials	
1	Do you review the HCP guide checklist when prescribing/dispensing Suliqua to a patient for the first time ?	 Never  Occasionally  Frequently
2	Do you review the HCP guide checklist when changing Suliqua pen strength to a patient for the first time ?	 Never  Occasionally  Frequently
3	Do you review each point of the checklist?	 Never  Occasionally  Frequently

Data: single punch per row

Key message:

HCPs should review the checklist that is in the guide to Healthcare professional when you prescribe /deliver Suliqua pens.

Q2b. Please answer to the following question related to the use of the Guide for patients and/or caregivers:

	Use of educational materials	
	Do you provide patients with patient guide prior initiating Suliqua	 Never  Occasionally  Frequently

Data: single punch per row

Key message:

HCPs should provide patients with the patient guide prior to prescribing or dispensing Suliqua.

Q3. According to your knowledge about the dose titration of Suliqua, which of the following statements are true and which are false?

	Prescription /Patient first daily dose/ dosage titration	TRUE	FALSE
1	Insulin-naive patients (on oral antidiabetic only), should start with 10 dose steps daily.	()	()
2	Patients who received between 20 and 30 units of insulin, should start with 30 dose steps daily.	()	()
3	Patients who received insulin or insulin glargine twice a day, should have a reduction of total daily dose of Suliqua by 10%.	()	()

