1	The dose pointer of the pen shows the number of dose steps to be injected	()	()
2	1 dose step of Suliqua contains 1 unit of insulin glargine 100U/ml plus a corresponding amount of lixisenatide	()	()
3	Even when the needle is changed, the pen should not be used by another person	()	()
4	You cannot use a syringe to withdraw Suliqua from a pre-filled pen	()	()
5	It is important to closely monitor your blood sugar level when starting Suliqua	()	()
6	One dose step of Suliqua only states the amount of lixisenatide	()	()

Data: single punch per row

Answer: Option 6 is false.

Q4. According to your knowledge, which of the following statements are true and which are false?
 Please select one answer per row.

		TRUE	FALSE
1	The prescription should mention which pre -filled pen you should use	()	()
2	The Suliqua (10-40) pen allows a daily injection of doses between 10 and 40 dose steps	()	()
3	The Suliqua (30-60) pen allows a daily injection of doses between 30 and 60 dose steps	()	()
4	If my total daily dose is more than 60 dose steps, then I should not use any of the Suliqua pens	()	()

Data: single punch per row

If S4=1 then skip item 3

If S4=2 then skip item 2

If S4= 3 then keep item 2 and item 3

Answer: All is true

Q5. Have you - or has the person you take care of - received the Suliqua Patient Guide from your physician or pharmacist? Please select one answer

Yes No

Data: single punch

Q6. Have you - or has the person you take care of - read the following educational materials (EM) related to Suliqua before using Suliqua? Please select one answer per row.

1	Suliqua Patient Guide (information that you may have received from your physician or pharmacist)	 Yes  No
2	Patient Information Leaflet (information available in each pack of Suliqua pre-filled pen)	 Yes  No

Data: single punch per row

If Q5=2 then skip item 1

Q7. Where would you - or the person you take care of - look for additional information if you have difficulties in understanding the prescription or use of the Suliqua pen ? You can select more than one answer.

	Prescription/ missing information	
1	Ask a physician	()
2	Ask a pharmacist	()
3	Ask a nurse	()
4	Read the Information Leaflet from the Suliqua package	()
5	Read the Suliqua Patient Guide	()
6	Read on the web	()

Data: multiple punch
If Q5=2 then skip item 5

Answer: all is true

Note :

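### As written, the proportion of patients who read the guide is computed among guide recipients only, although Section 8 asks for it among all patients/caregivers

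*Protocol*

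**What the plan says.** Protocol Section 8 lists, among the proportions to be assessed for patients/caregivers, those "Who read the patient guide before using SULIQUA pre-filled pen". The wording is not limited to people who were given the guide.

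The item that serves this objective is Q6 item 1 of the patient/caregiver questionnaire (Annex 3). Its routing instruction is "If Q5=2 then skip item 1". Q5 asks whether the guide was received from a physician or pharmacist. Its two boxes are Yes and No, so code 2 is taken to be No.

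Section 9.7 (general considerations) sets the rule for blanks: "Since, missing values are expected to be few and distributed at random, no replacement or imputation will be performed". It then adds "Missing values will not be considered in the denominators for proportions". The mock table in Section 9.7.1 gives missing answers a count but no percentage, and has no row for respondents who were not asked.

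The HCP questionnaire (Annex 2) has a parallel filter. Q2b, on handing out the patient guide, carries the instruction "Ask Q2b only if response to 2 is yes", where item 2 of Q1 is receipt of the patient guide. Section 9.3.1 lists distribution of the guide to patients as a yes/no variable for HCPs, again without limiting it to recipients.

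**The concern.** A patient who was not given the guide did not, in the ordinary course, read it. For the Section 8 objective that patient is a No. Under the routing the item is blank, and under the denominator rule the blank drops out. What remains is the proportion who read the guide among those who received it, which is a different quantity from the one the objective names.

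The premise behind the rule also fails for these blanks. They are not scattered item non-response: non-receipt produces all of them, and how many there are depends on how well delivery worked. Calling them not applicable instead of missing makes no difference, because the base is still recipients only unless the skip is recoded.

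At stake is one named objective, estimated in the favourable direction, with no direct estimate or confidence interval for the quantity asked for.

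**Working it through.** **Inputs.** From the protocol: the sample-size formula n = P(1−P)z²/e² with P = 50% (Section 9.5.1), 150 patients per wave for a half-width of 8%, and the routing and denominator rules above. Section 9.5.1 says the proportions of interest are those under the specific objectives, so the reading proportion is one of them. Not in the protocol, and therefore assumed: r, the share of patients who received the guide, taken as 50% to 90%; and c, the share of recipients who read it, taken as 70% to 90%.

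**Step 1: the plan's own figures.** With z = 1.96, 0.25 × 1.96² / 0.08² = 150.1, which matches 150. The HCP figures reproduce as well: 384.1 for a half-width of 5%, and 8.66% for 128 respondents.

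**Step 2: the two proportions.** Among recipients the proportion is c. Over all respondents, with non-recipients counted as not having read, it is r × c. The ratio is c/(r × c) = 1/r and the difference is c(1 − r).

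| r (assumed) | Reported, c = 80% | All patients, r × c | Difference | Ratio 1/r |
|---|---|---|---|---|
| 90% | 80% | 72% | 8 points | 1.11 |
| 80% | 80% | 64% | 16 points | 1.25 |
| 70% | 80% | 56% | 24 points | 1.43 |
| 50% | 80% | 40% | 40 points | 2.00 |

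Over the whole assumed grid, the difference runs from 7 points (r = 90%, c = 70%) to 45 points (r = 50%, c = 90%). It is zero only if every respondent received the guide.

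**Step 3: precision.** With 150 analysable patients in a wave, the recipients-only denominator is 150r. At the planning value of 50% the half-width is 1.96 × √(0.25/(150r)):

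- r = 90%, n = 135: 8.4%
- r = 80%, n = 120: 8.9%
- r = 70%, n = 105: 9.6%
- r = 50%, n = 75: 11.3%

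The stated value is 8.0%. The loss is relative to the same proportion on 150 respondents. At an observed 80%, for example, the half-width goes from 6.4% on 150 to 7.2% on 120 and 9.1% on 75.

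**Step 4: does it reach the success rule?** Patient success factor 3 combines Q6 (2 items) and Q7 (6 items) and requires 6 of 8. A patient without the guide is routed past Q6 item 1 and Q7 item 5, which leaves 8 − 2 = 6 items, all of which must be appropriate. HCP factor 3 requires 12 of 15. An HCP with neither guide is routed past the three Q2a items and Q2b, which leaves 15 − 4 = 11, so 12 is out of reach. Read literally, the fixed counts make a skip count against the respondent. The protocol does not say how the missing-value rule applies to these scores.

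**The case against.** The strongest reply is that non-delivery is visible elsewhere. Receipt is success factor 1 for both groups, acknowledging receipt is its own objective in Section 8, and results are stratified by country. A reader with r and c side by side can multiply them. This stands, and it rules out saying that failed delivery disappears from the report. It does not supply the estimate and interval for the objective as worded.

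A second reply is that the base for a filtered item is a table-shell matter for the SAP. That would hold if the protocol were silent. It is not silent: it fixes a denominator rule and gives a reason for it, and the reason does not fit these blanks. Section 9.7 does allow later revision of the analysis.

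Third, the sizes rest on assumed rates. That is so; only the factor 1/r is exact.

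A reader might also infer three stronger things that the documents do not support:

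- **That the effectiveness verdict is inflated.** The reading proportion is not one of the three success proportions, and in factor 3 the fixed item counts, taken literally, work the other way (Step 4).
- **That the reported figure looks best where delivery was worst.** The reported figure is c, which does not depend on r. Low receipt widens the gap to r × c but does not raise c.
- **That the HCP hand-out item misestimates an objective in the same way.** Handing out the patient guide is an entry in the variable list, not a Section 8 objective of its own. Q2b is also skipped by HCPs who cannot remember receiving the guide, and some of them may hand it out. Coding every skip as never handing it out would give only a lower bound.

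**Conclusion.** The point holds for the patient reading objective. As the protocol stands, the proportion reported for it is conditional on receipt and exceeds the all-patient proportion by 1/receipt. The relative excess is 10% or more once receipt is about 91% or lower (1/1.10 = 0.909). With an assumed 80% reading among recipients, the all-patient figure is 64% at 80% receipt and 40% at 50% receipt. At the planning proportion, the precision is worse than the stated 8% per wave.

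This rests on routed skips not being recoded, which nothing in the protocol provides for, and on non-recipients not having read the guide. The second is nearly but not strictly certain, because Q5 asks only about receipt from a physician or pharmacist. The all-patient figure may therefore be slightly low if some patients obtained the guide another way.

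The consequence is limited to the estimate for this objective. Receipt is reported on its own, and no inflation of the two-of-three success rule has been shown.

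**What to change.** In Section 9.7, state that items skipped by questionnaire routing are not missing values. For the Section 8 reading objective, code Q6 item 1 as No when Q5 is No, and report the proportion with its 95% CI over all analysable patient/caregiver respondents. Give the recipients-only figure in a second column labelled as such.

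For the HCP distribution variable (Section 9.3.1, Q2b), add an all-respondent figure as well. Count HCPs who answer No to Q1 item 2 as not distributing, and show those who do not remember as their own category, or give lower and upper bounds with them counted each way.

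The cost is a few lines of protocol or SAP text and one extra column. No new data are needed. The reading proportion will look less favourable wherever receipt is incomplete.

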9.2.3 Analysis population(s)

Analysable questionnaires are those submitted by the participant on the web, completed by phone or received by postal mail anonymously, and which do not have “I don’t know” as the answer to all questions. If the questionnaire is just filled on the web but not submitted, the questionnaire will be destroyed and will not be analysed.

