9.4 DATA SOURCES

The survey is a primary data collection conducted through two questionnaires administered by web, phone or paper:

- A HCP questionnaire (administered by web or phone)
- A patient questionnaire (administered by web or paper)

HCPs will be identified from OneKey lists (IQVIA).

The HCP questionnaire was developed and tested among 6 HCPs for its comprehensibility, consistency and the appropriateness of medical terms. HCPs' comments were implemented in the final version. Likewise, a patient/caregiver questionnaire was tested among 6 non-HCPs for optimal readability by patients.

The translated versions of the questionnaire from English into local languages was done using the back and forth method (from English into local language and then from local language back into English) to ensure an accurate translation.

The HCP and patient questionnaire completion is estimated to take about 15-20 minutes.

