9.7.2 Secondary analysis

Analysis of Participation rate

The following cases of total response and non-response will be identified and described for HCPs:

- Targeted HCPs: HCPs reached to whom an e-mail or e-mail has been sent or have been called
- Contacted HCPs: HCPs who have received the e-mail or have answered the phone call.
- HCPs who agreed to participate: HCPs willing to participate in the survey (e.g. by phone or by clicking on the link provided in the recruitment e-mail) or in the patient's recruitment
- HCPs with submitted questionnaire: HCPs who actually answered the questionnaire through the end and submitted it. (One or some missing answers are allowed across the questionnaire.)
- HCPs who recruited patients: HCPs with at least 1 patient having actually answered the questionnaire and submitted it by paper or web

For patients/caregivers, more simplified definitions will be calculated based on the following definitions:

- Contacted patients/caregivers: those who have been asked by HCPs to participate
- Patients/caregivers who agreed to participate: those who accepted the questionnaire
- Patients/caregivers with submitted questionnaire: those who actually answered the questionnaire and submitted it by paper or web

The participation rates of HCPs will be examined via the following ratios:

- Contact rate = Number of contacted HCPs divided by the total number of targeted HCPs
- Response rate = Number of HCPs who agreed to participate (in the survey or in recruitment of patients) divided by the total number of invited HCPs
- Cooperation rate = Number of HCPs with submitted questionnaire divided by the total number of HCPs who agreed to participate
- Refusal rate = (Number of contacted HCPs minus the number of HCPs who agreed to participate) divided by the total number of contacted HCPs

The participation rates will be presented by country and specialty.

The screening log which includes the HCPs' characteristics will enable to compare the participating and non-participating HCPs' profile to check if there is a selection bias.

Effect of EMs variations among targeted countries on success factors:

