9.8 QUALITY CONTROL

9.8.1 Data collection, validation and data quality control at IQVIA level

Data will be collected using a web or paper questionnaire.

The survey will be conducted according to the Standard Operating Procedures (SOPs) of IQVIA Primary Intelligence and IQVIA Real World Evidence Solutions.

For web version of the questionnaires, data will be collected using an electronic data capture system developed following a full validation process. A rigorous System Development Life Cycle (SDLC) is used for validation that complies with internal IT SOPs of Primary Intelligence (IQVIA). Unit testing and formal validation occur on all appropriate systems and components during the build stage. The SDLC is fortified with SOPs addressing validation for all clinical and risk management-related applications. The internet-based repository will be used to store survey data and, other relevant program information. Questions are programmed to ensure that they are asked in the appropriate sequence. Skip patterns are clearly indicated. Respondents cannot go back to a question once the question has been answered and they cannot skip ahead. Response options presented in a list are randomized to minimise positional bias. Programming will be reviewed by quality control and simulated users (User Testing) prior to implementation.

For the paper questionnaire, respondents will be asked to complete questionnaire thoroughly with a ball-point pen and will be informed that responses modified (deletion, overprint) by participants will be considered as missing. Questions will be ordered in a way that no response to one question is available later in the questionnaire. The questionnaire will use multiple visual elements together to improve skip pattern compliance.

Collected data will be entered and stored in a database specific to the survey and the country. A study database will be created by the merging of databases of each country. HCP identifying information will be stored separately from survey data.

Data will be checked in terms of consistency before data analysis:

- Removal of duplicates (if required)
- Data labelling and data formatting
- Range and consistency checks for each variable to identify potential non admissible values
- Cross-check the consistency of data for related variables (if feasible)

The study database will be locked once validated.

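### Missing answers leave the denominators as if random, but the scored true/false items have no don't-know option, so the rule can inflate some success proportions, and its effect on the scores is undefined

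*Protocol*

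**What the plan says.** **Missing-data rule (9.7, general considerations).** "Since, missing values are expected to be few and distributed at random, no replacement or imputation will be performed". The section then adds: "Missing values will not be considered in the denominators for proportions". Mock Table 4 in 9.7.1 follows this rule: its Missing row carries a count and no percentage.

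**Where missing values come from.** For the web form, 9.8.1 says: "Respondents cannot go back to a question once the question has been answered and they cannot skip ahead". For the paper form, the same section says that "responses modified (deletion, overprint) by participants will be considered as missing". The modes in 9.4 are "A HCP questionnaire (administered by web or phone)" and "A patient questionnaire (administered by web or paper)". Yet 9.7.2, in defining a submitted HCP questionnaire, says: "One or some missing answers are allowed across the questionnaire".

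**Analysable forms (9.2.3).** A submitted form is excluded only if it has a don't-know response "as the answer to all questions".

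**Success factors (9.7.1).** Factors 2 and 3 require at least 75% correct or appropriate answers. Each is also given as a count over a fixed total: 11 of 14 and 12 of 15 for HCPs, 8 of 10 and 6 of 8 for patients. The measures are deemed effective for a group if at least two of its three proportions reach 80%.

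**The concern.** The survey measures knowledge. In Annexes 2 and 3, patient Q3-Q4 and HCP Q3-Q4 allow only true or false. A don't-know option appears only at patient S4 (pen type), and a don't-remember option only at HCP Q1 (materials received). A paper respondent who does not know the answer can guess or leave the row blank. Blanks are therefore likely to be related to the outcome, and missing at random is an unsafe premise.

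The criterion in 9.2.3 offers no protection. No scored knowledge item has a don't-know answer, so no form can carry that answer throughout, and the criterion excludes nobody.

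The declaration of effectiveness rests on point proportions against 80%, with no margin. A modest upward bias can decide whether a factor passes. Section 9.7.2 also compares paper and web patients on the success factors, and blanks should arise mainly on paper, so the missing-data rule would act unequally on the two groups.

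**Working it through.** **1. The plan's thresholds.** Required count = 75% of items, rounded up.

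| Factor | Items | 75% | Count | Single-answer items among them |
|---|---|---|---|---|
| HCP understanding (Q3, Q4, Q7) | 5+5+4 = 14 | 10.5 | 11 | 10 (Q3, Q4) |
| HCP implementation (Q2a-b, Q5, Q6) | 4+7+4 = 15 | 11.25 | 12 | 4 (Q2a-b) |
| Patient understanding (Q3, Q4) | 6+4 = 10 | 7.5 | 8 | 10 |
| Patient implementation (Q6, Q7) | 2+6 = 8 | 6 | 6 | 2 (Q6) |

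All four stated counts reproduce. A missing answer can be recognised only in the single-answer items. In multiple-choice items an unticked box is itself a response. Exposure is therefore greatest in the understanding factors.

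**2. Effect of excluding respondents.** Let p be the reported success among respondents without a blank and d the share with a blank. The protocol gives no d, so it is assumed. If those with a blank count as not successful, the figure is p(1-d), and it falls below 80% when d > 1 - 0.80/p.

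| Reported p | d = 2% | d = 5% | d = 10% | Crosses 80% at d |
|---|---|---|---|---|
| 82% | 80.4% | 77.9% | 73.8% | 2.4% |
| 85% | 83.3% | 80.7% | 76.5% | 5.9% |
| 90% | 88.2% | 85.5% | 81.0% | 11.1% |

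Example with the planned 150 patients in a wave: 118 successes and 8 respondents with a blank give 118/142 = 83.1% if the 8 are excluded and 118/150 = 78.7% if counted.

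For patient factor 1 (one item) this is the direct calculation. For factors 2 and 3 it is an upper bound on the effect, because someone with one blank can still reach the count. If a share r of incomplete forms succeeds, the figure is p(1-d) + rd. With p = 82% and an assumed r = 40%, it is 0.90×82 + 0.10×40 = 77.8% at d = 10% and 0.85×82 + 0.15×40 = 75.7% at d = 15%. The crossing point is then (0.82-0.80)/(0.82-0.40) = 4.8%.

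**3. Three readings of the 10-item patient score.** Assume that each item is known with probability 0.7, that a share b of unknown items is left blank, and that the rest are guessed at 50%. Per item, P(correct) = 0.7 + 0.3(1-b)/2 and P(blank) = 0.3b; the pass rate is an exact multinomial sum over 10 items.

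| Reading | b = 0 | b = 10% | b = 25% |
|---|---|---|---|
| Fixed count of 8, all forms | 82.0% | 78.0% | 71.5% |
| 75% of answered items | 82.0% | 85.7% | 90.1% |
| Forms with any blank dropped | 82.0% | 84.7% | 88.8% |

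The same data fall on either side of 80% depending on the reading. These are heavy blank rates: the share of forms with at least one blank is 1 - 0.97^10 = 26% at b = 10% and 1 - 0.925^10 = 54% at b = 25%.

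For a single item at b = 25%, the proportion correct is 0.8125 over all respondents and 0.8125/0.925 = 0.878 over those who answered.

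**4. Designed skips.** Patients who name their pen at S4 see 9 of the 10 knowledge items. For 9 items the 75% rule gives 6.75, so 7, while the stated count stays at 8. At an assumed 80% correct per item, 73.8% reach 7 of 9 and 43.6% reach 8 of 9. Routed items therefore cannot be treated like blanks.

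**The case against.** The strongest reply is that factors 2 and 3 are counts over fixed totals. A respondent with blanks either reaches 8 of 10 or does not, stays in the denominator, and gets no credit for a blank. A reader might infer from 9.7 that the primary success proportions are inflated. The documents do not establish that. Inflation needs forms with blanks to be dropped or the 75% to be taken over answered items, and 9.7.1 states neither. What remains is that 9.7 covers proportions in general, the factors are defined as proportions, and each is worded both as a percentage of answers and as a count.

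A reader might also infer that only paper forms can contain blanks. Section 9.8.1 points that way, but 9.7.2 allows missing answers in HCP forms, which are web or phone only. The two passages must be reconciled.

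Further points that stand:
- HCP don't-remember answers at Q1 are recorded responses, so the missing-data rule does not remove them.
- All blank rates above are assumptions. Effectiveness needs only two of three factors, so one factor falling below 80% need not reverse the conclusion.
- Missing counts will be reported, and 9.7.2 will describe completeness by paper and web. This makes the problem visible but does not settle the primary figure.
- Detail may follow in the SAP. However, the denominator rule and its justification are already fixed in the protocol.

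**Conclusion.** The point holds as a badly justified rule with an undefined effect on the scores, not as a demonstrated inflation of every success proportion.

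- **Item-level results and patient factor 1:** the answered-only denominator applies as written and can bias these upward.
- **Factors 2 and 3:** inflated under two of the three readings and not under the fixed count. The protocol leaves the choice open.
- **Size:** conditional on assumed blank rates. If respondents with a blank are excluded rather than counted as not successful, about 2.4% of such forms is enough to hide a true figure below 80% behind a reported 82%, and about 5.9% behind a reported 85%. For factors 2 and 3 more forms are needed if some incomplete ones would reach the count anyway.
- **Section 9.2.3:** the don't-know criterion is inoperative whatever the blank rate.

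The change should be made before the success factors are computed.

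**What to change.** In 9.7:
- For factors 2 and 3, keep every analysable questionnaire in the denominator. Count an unanswered or voided applicable single-answer item as not correct.
- Score multiple-choice items (HCP Q5-Q7, patient Q7) as ticked or unticked against the key, so that leaving a wrong option unticked is correct. The key for HCP Q6 lists options 1, 3 and 4 as mandatory and is silent on option 2; it needs completing.
- Treat items skipped by routing (patient S4 and Q5, HCP Q1) as not applicable, and apply the 75% to the applicable items. For patients this means 7 of 9 for understanding when S4 names a pen, and 5 of 6 for implementation when Q5 is No. For HCP implementation it means 11 of 14, 9 of 12 or 9 of 11, depending on which of Q2a and Q2b is skipped.
- For patient factor 1, count a blank at Q5 as not received.
- Report the answered-only result as a sensitivity analysis.

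In 9.2.3, define an analysable form as one submitted with at least one scored item answered. Reconcile 9.7.2 with 9.8.1 on whether web and phone forms can contain missing answers.

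The cost is a few lines of text and rescoring. The questionnaires stay as they are, which matters because Wave 1 collection began in September 2019. Success figures may be slightly lower. The paper-versus-web comparison will need a caveat: web respondents must guess and gain some credit by chance, while paper blanks score nothing and some voided paper answers may be genuine corrections.
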